7.1.1.1.4 Hepatic Insufficiency

For subjects with baseline chronic hepatic impairment (mild, moderate), reduce the starting and subsequent doses of carfilzomib by 25% (Brown et al, 2017):

- 15 mg/m^2 day 1 of cycle 1 and 42 mg/m^2 day 8 of cycle 1 and thereafter.

If hepatic function returns to normal, the dose may be re-escalated to 56 mg/m^2 after the first cycle. For dose modification due to subsequent changes in hepatic function, refer to Section [7.4.1.1.2](#).

Mild and moderate hepatic dysfunction is defined as:

- Mild: elevated bilirubin > 1.0 but $\leq 1.5 \times \text{ULN}$ or normal bilirubin with any elevation of AST
- Moderate: elevated bilirubin > 1.5 but $< 3 \times \text{ULN}$

7.1.1.2 Pomalidomide

7.1.1.2.1 Dosage Formulation

Pomalidomide will be manufactured and packaged by Celgene.

Pomalidomide is initially supplied as a 4-mg capsule, and supplied as a 3 mg, 2 mg, or 1 mg capsule if dose modification is required (refer to Pomalyst[®] Prescribing Information or Imnovid[®] SmPC for more details).

7.1.1.2.2 Dosage, Administration, and Schedule

Pomalidomide dose will be 4 mg per day orally on days 1 to 21 of each cycle until progression.

The planned dose (mg), dose administered (mg), start date, stop date, reason for dose change/withheld, reason for dose delay, are to be recorded on each subject's eCRF.

7.1.1.2.3 Hepatic Insufficiency

For subjects with mild or moderate hepatic impairment, (Child-Pugh classes A or B), the recommended starting dose is 3 mg daily (25% dose reduction). For subjects with severe hepatic impairment (Child-Pugh class C), the recommended dose is 2 mg (50% dose reduction). See Section [12.12](#).

7.1.2 Non-investigational Products

7.1.2.1 Dexamethasone: Dosage, Administration, and Schedule

Dexamethasone, a non-Amgen non-investigational product, will also be used in this study (Dexamethasone SmPC and USPI). Dexamethasone will be administered at least 30 minutes, but no more than 4 hours prior to carfilzomib on days of carfilzomib administration.

Dexamethasone will be administered at a dose of 40 mg on days 1, 8, 15, and 22 of each 28-day cycle up to progression during cycles 1 to 12.

Dexamethasone will be administered at a dose of 20 mg on days 1 and 15 of each 28-day cycle up to progression during cycles 13 onward.

For subjects \geq 75 years of age, the dose will be 20 mg during cycles 1 through 12 and 10 mg from cycles 13 onward.

The planned dose (mg), dose administered (mg), start date/time, stop date/time, route, reason for dose change/withheld, reason for dose delay, reason for dose interruption are to be recorded on each subject's eCRF.

7.1.3 Medical Devices

There are no investigational medical devices being used in this study.

Other non-investigational medical devices may be used in the conduct of this study as part of standard care.

Non-Amgen non-investigational medical devices (eg, syringes, sterile needles), that are commercially available are not usually provided or reimbursed by Amgen (except, for example, if required by local regulation). The investigator will be responsible for obtaining supplies of these devices.

7.1.4 Other Protocol-required Therapies

All other protocol-required therapies including, antiviral prophylaxis, and proton pump inhibitor or protocol recommended therapies including thromboprophylaxis, tumor lysis syndrome prophylaxis, bone preserving therapy, prophylaxis for *Pneumocystis jirovecii* pneumonia, and for at-risk subjects, prophylaxis for Hepatitis B virus reactivation that are commercially available are not provided or reimbursed by Amgen (except if required by local regulation). The investigator will be responsible for obtaining supplies of these protocol-required therapies.

7.1.4.1 Antiviral Prophylaxis

An antiviral is a required concomitant medication for the duration of treatment with carfilzomib. Acyclovir, famciclovir, or valacyclovir should be administered per institutional standards, dose adjustments for renal function where appropriate, initiated within 1 week of the first dose of carfilzomib and should continue for the duration of treatment with carfilzomib.

7.1.4.2 Proton-pump Inhibitor

Proton-pump inhibitor (omeprazole or equivalent) is required while on high-dose dexamethasone (40 mg or 20 mg weekly).

7.1.4.3 Thromboprophylaxis

It is strongly recommended that all subjects receive thromboprophylaxis (eg, enteric-coated aspirin at standard prophylactic dose or other antiplatelet such as clopidogrel bisulfate or anticoagulant medication, such as low molecular weight heparin or warfarin). In addition, second thromboprophylaxis medication is strongly recommended in subjects with elevated risk of thrombosis, based on an individual benefit/risk assessment (Li et al, 2017).

7.1.4.4 Tumor Lysis Syndrome Prophylaxis or Therapy

An approved uric acid-lowering agent (eg, allopurinol) in subjects at high-risk for tumor lysis syndrome (TLS) due to high tumor burden may be prescribed at the investigator's discretion, according to the package insert.

Subjects should be well hydrated to reduce the risk of TLS and decline in renal function; refer to the current Carfilzomib IB for safety guidance regarding TLS.

7.1.4.5 Bone Preserving Therapy / Bone Targeting Agents

Bone preserving therapy or bone targeting agents are strongly recommended for all subjects with evidence of lytic destruction of bone or with osteopenia (Gralow et al; 2013; Terpos et al, 2013). Commercially available therapies are preferred when available and should be used for subjects with osteolytic or osteopenic myelomatous bone disease according to the manufacturer's recommendations, as described in the prescribing information.

Subjects who are using bone preserving therapy or bone targeting agents when they enter the study should continue the same treatment. Subjects with evidence of lytic destruction of bone or with osteopenia who are not using a bone preserving therapy at the time of enrollment should start therapy as soon as possible during cycle 1 or 2 of treatment. Investigators should not start bone preserving therapy or bone targeting agents during the study, unless it has been agreed with the sponsor that there is no sign of disease progression.

7.1.4.6 Prophylaxis for *Pneumocystis Jiroveci*

Pneumocystis jiroveci pneumonia prophylaxis should be considered, as per institutional guidelines while on dexamethasone.

7.1.4.7 Prophylaxis for Hepatitis B Virus Reactivation

Hepatitis B virus reactivation prophylaxis should be considered for subjects at risk (ie, subject tested positive on serology or had a prior history of HBV infection) as per institutional standards.

7.1.4.8 Other Permitted Therapies

The following medications and supportive therapies are examples of support therapies that may be used during the study:

- antivirals
- medications to control hyperglycemia
- medications to prevent constipation (eg, adequate hydration, high-fiber diet, and stool softeners, if needed)
- prophylactic antiemetics, with the exception of corticosteroids
- granulocyte colony stimulating factors (as clinically indicated; may be used prophylactically after cycle 1), erythropoietin, and transfusion of platelets and red blood cells (RBCs)
- loperamide is recommended for the treatment of diarrhea, starting at the time of the first watery stool. The loperamide dose and regimen is according to institutional guidelines. Prophylactic loperamide is not recommended.

7.1.5 Other Treatment Procedures

No other treatment procedures are required.

7.1.6 Product Complaints

A product complaint is any written, electronic or oral communication that alleges deficiencies related to the identity, quality, durability, reliability, safety, effectiveness, or performance of a drug, **combination product**, or device after it is released for distribution to market or clinic by either (1) Amgen or (2) **distributors or partners** for whom Amgen manufactures the material. **This includes all components distributed with the drug, such as packaging drug containers, delivery systems, labeling, and inserts.**

This includes any investigational or non-investigational products provisioned and/or repackaged/modified by Amgen.

. carfilzomib

. pomalidomide

Any product complaint(s) associated with an investigational product or non-investigational products(s) supplied by Amgen are to be reported according to the instructions provided in the IPIM or study manual.

Product complaints must be reported to Amgen within 24 hours.

7.1.7 Excluded Treatments, Medical Devices, and/or Procedures During Study Period

7.1.7.1 Anticancer Therapeutic or Radiation

Concurrent therapy with a marketed or investigational anticancer therapeutic or radiation to large marrow reserves for either a palliative or therapeutic intent is excluded.

7.1.7.2 Plasmapheresis

Plasmapheresis is not permitted during screening and at any time while the subject is receiving study treatment. For subjects requiring plasmapheresis while on study treatment, every attempt should be made to document disease status by IMWG criteria first. Study treatment must be discontinued.

7.1.7.3 Corticosteroids

Long-term corticosteroids for nonmalignant conditions (eg, asthma, inflammatory bowel disease) equivalent to a dexamethasone dose > 4 mg/day or prednisone > 20 mg/day are not permitted. Corticosteroids given short-term (up to 2 weeks) for non-malignant conditions are permitted provided that the cumulative dose is less than 40 mg per week dexamethasone equivalent (less than 20 mg dexamethasone equivalent for subjects \geq 75 years of age). Medical monitor should be contacted if short-term corticosteroid use is required > 2 weeks or at cumulative dose of more than 40 mg dexamethasone equivalent or 20 mg for subjects \geq 75 years of age.

7.1.7.4 Prohibited Therapies

Use of the treatments listed below is prohibited during the study:

- Subjects may not receive treatment with an investigational drug or device while participating in this study
- During cycle 1, the prophylactic use of hematopoietic growth factors is prohibited
- Other agents that target CD38
- Medications used for other indications that have antimyeloma properties (for example, interferon and clarithromycin (Ghosh et al, 2014))
- Administration of approved or investigational treatments for multiple myeloma (including but not limited to conventional chemotherapies, IMiDs, or proteasome inhibitors other than those agents that are part of the regimen for which the subject was enrolled)
- Concomitant administration of investigational agents is prohibited. Administration of commercially available agents with activity against or under investigation for multiple myeloma are not permitted

Continuation of study drug during or after emergency orthopedic surgery or radiotherapy because of subject benefit may only occur in the absence of disease progression and after consultation with and approval by the sponsor. Such emergency radiotherapy may consist of localized radiotherapy for pain control or for stabilization of an extensive bone lesion at high risk of pathologic fracture or damage to surrounding tissues in a subject in whom delay of systemic therapy is not appropriate. Such radiotherapy is to occur within the first 2 cycles of treatment and the absence of evidence of disease progression is to be reviewed and approved by the sponsor.

The sponsor must be notified in advance (or as soon as possible thereafter) of any instances in which prohibited therapies are administered.

7.2 Method of Treatment Assignment

Subjects who meet eligibility criteria will be treated with KPd.

7.3 Blinding

This is an open-label study; blinding procedures are not applicable.

7.4 Dose Modification

7.4.1 Dosage Adjustments, Delays, Rules for Withholding or Restarting, Permanent Discontinuation

7.4.1.1 Amgen Investigational Product: Carfilzomib

Carfilzomib will be discontinued, temporarily delayed, or dosage temporarily reduced, in the event of a treatment-related toxicity that, in the opinion of the investigator, warrants the discontinuation, temporary delay or dose reduction as indicated in [Table 7-2](#) and [Table 7-3](#) (refer to [Table 7-5](#) and [Table 7-6](#) for KPd pomalidomide dosage adjustments).

Dose reduction levels of carfilzomib for toxicity management of individual subjects are provided in [Table 7-1](#). Subjects who require a dose level reduction and tolerate the reduced dose for 1 full cycle may at the discretion of the treating physician increase the dose to a prior dose starting with the next cycle except when the dose reduction is due to: pulmonary hypertension, pulmonary toxicity, grade 3 or worse cardiac failure, or drug-induced hepatotoxicity.

Table 7-1. Dose Decrements for Carfilzomib

Nominal Dose (mg/m ²)	Reduced Carfilzomib Doses (mg/m ²)			
	Dose -1	Dose -2	Dose -3	Dose -4
20 ^{a, b}	15	11	Discontinue	-
56	45	36	27	20

^a If dose reduction of carfilzomib is required on cycle 1 day 1, the investigator should contact the medical monitor to discuss the situation before any additional doses of carfilzomib are administered.

^b For subjects with baseline chronic hepatic impairment (mild, moderate), reduce the starting and subsequent doses of carfilzomib by 25% (ie, 15 mg/m² day 1 of cycle 1 and 42 mg/m² on day 8 of cycle 1 and thereafter).

The subject will be considered on protocol treatment while receiving carfilzomib or pomalidomide.

If day 1 of a cycle is delayed, all subsequent doses within the cycle and day 1 of subsequent cycles should be adjusted accordingly to maintain the 28-day cycle duration. However, if a within-cycle dose is delayed, then the dates of the subsequent within-cycle doses should not be adjusted. For within-cycle doses, if administration does not commence within the allowable window of the scheduled administration date, then the dose will be considered a missed dose. Administration may resume at the next planned dosing date. A missed dose will not be made up. There should be a minimum of 5 days between carfilzomib doses.

If a subject requires interruption of carfilzomib for more than 6 consecutive weeks due to unresolved toxicities, the subject must be discontinued permanently from carfilzomib.

The reason for dose change of carfilzomib is to be recorded on each subject's eCRF.

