- 230 Major surgery (except kyphoplasty) within 28 days prior to enrollment
- 231 Autologous or allogeneic stem cell transplant within 90 days prior to enrollment

Prior/Concurrent Clinical Study Experience

- 232 Currently receiving treatment in another investigational device or drug study, or less than 28 days since ending treatment on another investigational device or drug study(ies). Other investigational procedures while participating in this study are excluded.

Diagnostic Assessments

- 233 Calculated or measured creatinine clearance < 30 mL/min (calculation must be based on the Cockcroft and Gault formula) within 28 days prior to enrollment
- 234 Hepatic dysfunction within 28 days prior to enrollment:
 - bilirubin > 1.5 x the upper limit of normal (ULN)
 - aspartate aminotransferase (AST) or alanine aminotransferase (ALT) > 3 x ULN
- 235 Left ventricular ejection fraction < 40% assessed by transthoracic ECHO
- 236 Absolute neutrophil count (ANC) < $1 \times 10^9/L$ within 28 days prior to enrollment. Screening ANC should be independent of granulocyte- and granulocyte macrophage-colony stimulating factor support for at least 1 week and of pegylated granulocyte stimulating factor for ≥ 2 weeks
- 237 Hemoglobin < 80 g/L within 28 days prior to enrollment. Subjects should not have received red blood cell (RBC transfusions) for at least 7 days prior to obtaining the screening hemoglobin.
- 238 Platelet count < $50 \times 10^9/L$ ($\leq 30 \times 10^9/L$ if plasma cell percentage in the bone marrow is $\geq 50\%$) within 28 days prior to start of treatment

Subjects should not have received platelet transfusions for at least 7 days prior to obtaining the screening platelet count.

Other Exclusions

- 239 Pregnant or breastfeeding female subjects or female subjects who are planning to become pregnant or breastfeed during treatment and for an additional 30 days after the last dose of carfilzomib or pomalidomide (whichever occurs latest).
- 240 Female subjects of childbearing potential unwilling to use 2 methods of contraception (1 of which must be highly effective; see Section 12.5) during the study and for an additional 30 days after the last dose of carfilzomib or pomalidomide (whichever occurs latest). Additionally, subjects unwilling to use contraception at least 28 days prior to initiating treatment. Refer to Section 12.5 for additional contraceptive information.

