PD or death > 70 days after last visit	Last visit prior to PD or death; otherwise, first dose date of any study treatment ^a	Censored
PD or death, no prior new anticancer therapy	Earlier of PD or death ^b	Event
No PD, new anticancer treatment, death	Last visit prior to new treatment; otherwise, first dose date of any study treatment ^b	Censored

“Visit” refers to a post-baseline evaluable disease assessment.

^aIf new anticancer therapy starts prior to PD or death, PFS will be censored at the earliest of the following: (a) the last evaluable disease assessment prior to subsequent anticancer therapy, or (b) the last non-NE, post-baseline assessment followed > 70 days later by disease progression or death; otherwise, first dose date.”

^bPFS will be censored if PD or death > 70 days after last evaluable disease assessment.

Relative Dose Intensity

RDI reflects whether the dose intensity of a therapy was implemented as planned. It will be calculated as the ratio of actual dose intensity relative to planned dose intensity

$$\text{Relative Dose Intensity (RDI)} = \frac{\text{Actual dose intensity}}{\text{Planned dose intensity}}$$

For carfilzomib: Actual dose intensity is defined as the actual amount of drug in mg/m² delivered to a subject per week of treatment.

$$\text{Actual Dose Intensity (mg/m}^2\text{/week)} = \frac{\text{Actual cumulative dose (mg/ m}^2\text{)}}{\text{Number of weeks of actual treatment}}$$

Actual cumulative dose in (mg/m²) is the sum of received doses (mg) divided by baseline body surface area (BSA) (m²) of the patient. Each subject's first dose of carfilzomib will be calculated based upon baseline BSA using the Mosteller formula. The dose for each subject should not be revised unless the subject experiences a change in body weight of > 20% in which case the BSA and dose should be recalculated. The recalculated BSA becomes the new baseline and is used in dose calculation. BSA will be capped at 2.2 for carfilzomib. Number of weeks of actual treatment will be calculated as (Last Dose Date of carfilzomib – First Dose Date of carfilzomib + i) / 7. When the last cycle is among cycles 1 to 12, i = 7 if the last infusion is given on day 1 or 8 within the last cycle, i = 14 if the last infusion is given on day 15. When the last cycle is among cycles 13+, i = 14 if the last infusion is given on day 1 or day 15 within the last cycle.

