Planned dose intensity is defined as the planned amount of carfilzomib in mg/m² delivered to a subject per week of treatment.

$$\text{Planned Dose Intensity (mg/m}^2\text{/week)} = \frac{\text{Planned cumulative dose (mg/ m}^2\text{)}}{\text{Number of protocol specified treatment weeks}}$$

It will be calculated as the planned cumulative dose of carfilzomib in mg/m² divided by the planned number of weeks for the treatment per protocol based on the corresponding cycle and day of the last carfilzomib infusion. Per protocol, one cycle is 28 days (4 weeks), so the planned number of treatment weeks will be calculated as 4 x (c-1) + j, where c is the cycle in which the last carfilzomib infusion is given. When c is less than or equal to 12, j = 1 if the last carfilzomib infusion is given on day 1 within the last cycle, j=2 if the last infusion is given on day 8, j=4 if the last infusion is given on day 15. When c is greater than or equal to 13, j=2 if the last infusion is given on day 1 within the last cycle, j=4 if the last infusion is given on day 15. The planned cumulative dose of carfilzomib is the summation of planned carfilzomib dose (mg/m²) per week as: [20, 56, 56, 0] in cycle 1, [56, 56, 56, 0] in cycle 2 to 12 and [56, 0, 56, 0] in cycle 13 onwards, across the planned number of treatment weeks.

For dexamethasone: Actual dose intensity is the actual amount of drug in mg delivered to a subject per week of treatment.

$$\text{Actual Dose Intensity (mg/week)} = \frac{\text{Actual cumulative dose (mg)}}{\text{Number of weeks of actual treatment}}$$

The cumulative dose in mg is the summation of total quantity administered (mg) over the study. Number of weeks of actual treatment will be calculated as (Last Dose Date of dexamethasone – First Dose Date of dexamethasone + i)/7. When the last cycle is among cycle 1 to 12, i=7 if the last dexamethasone dose is given on day 1, 8, 15, or 22. When the last cycle is among cycle 13+, i = 14 if the last dexamethasone dose is given on day 1 or day 15 within the last cycle. Planned dose intensity (mg/week) is defined as the planned amount of dexamethasone in mg delivered to a subject per week of treatment.

$$\text{Planned Dose Intensity (mg/week)} = \frac{\text{Planned cumulative dose (mg)}}{\text{Number of protocol specified treatment weeks}}$$

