It will be calculated as the planned cumulative dose of dexamethasone in mg divided by the planned number of weeks for the treatment per protocol based on the corresponding cycle and day of the last dexamethasone dose. Per protocol, one cycle is 28 days (4 weeks), so the planned number of treatment weeks will be calculated as $4 \times (c-1) + j$, where c is the cycle in which the last dexamethasone dose is given. When c is less than or equal to 12, j =1 if the last dexamethasone dose is given on day 1 within the last cycle, j=2 if the last dose is given on day 8, j=3 if the last dose is given on day 15, j=4 if the last dose is given on 22. When c is greater than or equal to 13, j=2 if the last dose is given on day 1, j=4 if the last dose is given on day 15. The planned cumulative dose of dexamethasone is the summation of planned dexamethasone dose (mg) per week as: [40, 40, 40, 40] in cycle 1 to12 (20 mg for subjects >75 years of age) and [20, 0, 20, 0] in cycle 13 onwards (10mg for subjects > 75 years age), across the planned number of treatment weeks.

For pomalidomide: Actual dose intensity is the actual amount of drug in mg delivered to a subject per week of treatment.

$$\text{Actual Dose Intensity (mg/week)} = \frac{\text{Actual cumulative dose (mg)}}{\text{Number of weeks of actual treatment}}$$

The cumulative dose in mg is the summation of total quantity administered (mg) over the study. Number of weeks of actual treatment will be calculated as (Last Dose Date of

pomalidomide – First Dose Date of pomalidomide + $i/7$, where the value of i depends on the day of the cycle on which the last pomalidomide is taken, which is shown in the table below.

The last pomalidomide dose day in the cycle	Value of i
Day 1 or Day 8	7
Day 2 or Day 9	6
Day 3 or Day 10	5
Day 4 or Day 11	4
Day 5 or Day 12	3
Day 6 or Day 13	2
Day 7 or Day 14	1
Day 15 to Day 28	14 – (Day # - 15)

Planned dose intensity (mg/week) is defined as the planned amount of pomalidomide in mg delivered to a subject per week of treatment.

$$\text{Planned Dose Intensity (mg/week)} = \frac{\text{Planned cumulative dose (mg)}}{\text{Number of protocol specified treatment weeks}}$$

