It will be calculated as the planned cumulative dose of pomalidomide in mg divided by the planned number of weeks for the treatment per protocol based on the corresponding cycle and day of the last pomalidomide infusion. Per protocol, one cycle is 28 days (4 weeks), so the planned number of treatment weeks will be calculated as $4 \times (c-1) + j$, where c is the cycle in which the last pomalidomide dose is taken and $j=1$ if the last pomalidomide dose is taken on day 1 to 7 within the last cycle, $j=2$ if the last dose is given on day 8 to 14, $j=4$ if the last dose is given on day 15 to 21. The planned cumulative dose of pomalidomide is the summation of planned pomalidomide dose (mg) per week ($[7 \times 4, 7 \times 4, 7 \times 4, 0]$) across the planned treatment weeks.

Revised International Staging System (R-ISS) Stage at Baseline

R-ISS stage at baseline will be calculated using ISS, risk group by FISH, and LDH, based on the criteria published by the International Myeloma Working Group ([Palumbo, 2015](#)):

Stage I: ISS stage I and standard risk group by FISH and normal LDH

Stage II: Not R-ISS stage I or III

Stage III: ISS stage III and {either high-risk group by FISH or high LDH}

Sustained MRD[-]CR Rate

Sustained MRD[-]CR rate is defined as the proportion of subjects that maintain MRD[-]CR for 12 months +/- 4 weeks or more, ie, maintaining MRD[-]CR for at least 12 months minus 4 weeks is considered as sustained, after achieving MRD[-]CR status among the subjects who reach the MRD[-]CR status, disregarding when the first MRD[-]CR was reached.

Sustained MRD[-]CR Rate at 24 months

Sustained MRD[-]CR rate at 24 months is defined as the proportion of subjects that maintain MRD[-]CR for 12 months +/- 4 weeks or more, ie, maintaining MRD[-]CR for at least 12 months minus 4 weeks is considered as sustained, after achieving MRD[-]CR status in the time window of **Key Secondary** endpoint assessment.

Time to Response

Time from start of treatment to first date of confirmed PR or better.

Time to Response = (response start date – start of **any study** treatment date + 1) / 30.4

Time (month) since initial diagnosis

Time since initial diagnosis is defined as:

(Date of informed consent signed - date of first diagnosis of MM + 1) / 30.4

Treatment-emergent Adverse Event

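### The SAP plans 20 then 56 mg/m² of carfilzomib for every subject, so a subject kept on the protocol's hepatic dose of 42 mg/m² has a relative dose intensity of 75% with no dose missed

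*Protocol*

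**What the plan says.** **Protocol, carfilzomib.** Section 7.1.1.1.4 and footnote b of Table 7-1 cover subjects with mild or moderate chronic hepatic impairment at baseline. Sites are to "reduce the starting and subsequent doses of carfilzomib by 25"%, which the protocol writes out as 15 mg/m² on cycle 1 day 1 and 42 mg/m² from cycle 1 day 8. Section 7.1.1.1.4 adds: "If hepatic function returns to normal, the dose may be re-escalated to 56" mg/m², after the first cycle.

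**Protocol, who can enter.** Section 7.1.1.1.4 defines mild impairment as bilirubin above 1.0 and up to 1.5 × ULN, or normal bilirubin with any AST elevation. Moderate starts above 1.5 × ULN. Exclusion 234 bars bilirubin above 1.5 × ULN and AST or ALT above 3 × ULN.

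**Protocol, pomalidomide.** Section 7.1.1.2.3 recommends, rather than requires, a 3 mg start for Child-Pugh class A or B.

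**SAP section 5, Relative Dose Intensity.** The stated purpose is: "RDI reflects whether the dose intensity of a therapy was implemented as planned". The planned carfilzomib doses by week are 20, 56, 56, 0 in cycle 1, then ["56, 56, 56, 0] in cycle 2 to 12 and [56, 0, 56, 0] in cycle 13 onwards". No hepatic schedule appears. Planned pomalidomide is 4 mg on each of 21 days for all subjects. Planned dexamethasone is lowered by age ("20 mg for subjects >75 years of age" in cycles 1 to 12).

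**SAP 9.6.8.** Dose intensity is part of the exposure summary, and the reader is sent to section 5 for its definition.

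**The concern.** The 15/42 mg/m² schedule is the regimen that the protocol assigns from day 1 to these subjects. It is not a response to toxicity. A denominator of 20/56 mg/m² scores correct dosing as a shortfall, so the RDI summary mixes protocol-assigned dosing with missed doses and true reductions. It also departs from what the SAP does for dexamethasone, where a lower dose assigned by the protocol counts as planned. At stake is how the delivery of carfilzomib is described in this group, and slightly in the whole cohort.

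**Working it through.** **1. The protocol's hepatic doses.** 0.75 × 20 = 15 and 0.75 × 56 = 42 mg/m². Both match.

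**2. RDI formula (SAP section 5).** RDI = (actual cumulative dose ÷ actual weeks) ÷ (planned cumulative dose ÷ planned weeks).

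**3. Weeks.** Take a subject on schedule whose last infusion is cycle 12 day 15.
- Actual: that infusion falls 11 × 28 + 14 = 322 days after the first, and the SAP adds 14, so (322 + 14)/7 = 48.
- Planned: 4 × (12 − 1) + 4 = 48.

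The weeks cancel, and RDI is the ratio of cumulative doses.

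**4. Kept on 42 mg/m² for 12 cycles.**
- SAP plan: 20 + 56 + 56 + 11 × 168 = 1980 mg/m².
- Assigned and received: 15 + 42 + 42 + 11 × 126 = 1485 mg/m².
- RDI = 1485/1980 = 75.0%.

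Every assigned dose is 0.75 of the SAP dose, so the result does not depend on when treatment stops: 99/132 at cycle 1, 729/972 at cycle 6 and 1989/2652 at cycle 18 are all 75.0%. A subject without impairment who is dosed on schedule scores 100%.

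**5. Re-escalated to 56 mg/m² from cycle 2.**

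| Cycles | Received | SAP plan | RDI |
|---|---|---|---|
| 2 | 99 + 168 = 267 | 300 | 89.0% |
| 6 | 99 + 5 × 168 = 939 | 972 | 96.6% |
| 12 | 99 + 11 × 168 = 1947 | 1980 | 98.3% |

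**6. Effect on the cohort mean.** Each subject kept on 42 mg/m² lowers the mean of 52 by 25/52 = 0.48 points. The documents do not give the number affected. Assuming 1, 3, 5 or 10 such subjects, the mean falls by 0.5, 1.4, 2.4 or 4.8 points.

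**7. Pomalidomide, separately.** A subject started on 3 mg who takes every dose scores (3 × 21)/(4 × 21) = 75.0%.

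**8. Corrected denominator.** With the assigned 15/42 mg/m² schedule as the plan, the subject in step 4 scores 1485/1485 = 100%.

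**The case against.** The best defence is that RDI against a nominal full dose is a recognised convention and that the SAP prints its planned doses for anyone to see. But the SAP never says that it means a nominal dose. It says that RDI shows whether the plan was carried out, and its dexamethasone plan follows the lower dose that the protocol assigns.

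That comparison has a limit. Age-based dexamethasone dosing is permanent and part of the base regimen, whereas hepatic carfilzomib dosing is conditional and reversible. This justifies a plan that changes at re-escalation. It does not justify planning 56 mg/m² for someone assigned 42.

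Two limiting points stand in full. Actual dose intensity in mg/m² per week does not use the planned dose, and dose reductions are tabulated with reasons, so the exposure section as a whole is not distorted. The affected group is also probably small: exclusion 234 in practice leaves only mild impairment.

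Stronger readings are tempting but not supported:
- **That Table 7-1 gives no step below 42 mg/m².** Its 56 mg/m² row lists 36, 27 and 20. What is missing is a row that starts from 42. Since 45 would be an increase, 36 is the natural next step.
- **That such subjects would leave the Per Protocol Set under deviation code 503** (carfilzomib dose not adjusted per protocol). Nothing suggests that a step from 42 to 36 would be coded that way.
- **That everyone starting on the hepatic dose scores 75%.** This holds only without re-escalation.
- **That the carfilzomib hepatic group is also the 3 mg pomalidomide group.** Carfilzomib uses bilirubin and AST, pomalidomide uses Child-Pugh class, and 3 mg is a recommendation. Planning 3 mg for a subject properly taking 4 mg would give 4/3 = 133%.

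**Conclusion.** The carfilzomib RDI rule gives a wrong result, as written, for a subject with baseline hepatic impairment: 75.0% instead of 100% if kept on 42 mg/m², or 96.6% at 6 cycles and 98.3% at 12 if re-escalated from cycle 2. These figures assume dosing on schedule with no missed doses. The severity is minor. RDI is descriptive, and no test, endpoint or power figure uses it. A reader might infer that the efficacy results are at risk. They are not: ORR and MRD[-]CR are analysed on the Safety Analysis Set without reference to dose intensity. The cohort effect rests on an unknown count, at 0.48 points of mean RDI per subject kept on 42 mg/m² out of 52.

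**What to change.** In SAP section 5:
- **Carfilzomib.** For subjects assigned the hepatic dose at baseline, plan [15, 42, 42, 0] in cycle 1, [42, 42, 42, 0] in cycles 2 to 12 and [42, 0, 42, 0] from cycle 13, changing to 56 from the date of any permitted re-escalation. The 25% cuts in Table 7-3 for liver dysfunction arising on study remain counted as reductions.
- **Pomalidomide.** Plan 3 mg only for subjects actually started on 3 mg under the Child-Pugh rule in Protocol 7.1.1.2.3.

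If the sponsor prefers a nominal denominator, it should say so and report how many subjects started on each hepatic dose.

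Optionally, a footnote to Table 7-1 could state that decrements from 42 mg/m² go to 36, 27 and 20.

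The cost is a few lines of text and a small programming change. The eCRF already records planned and administered doses for both drugs (Protocol 7.1.1.1.2 and 7.1.1.2.2), so no new data are needed.
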